9.3.2 Pharmacokinetic Statistical Inference

The “PK” population for the statistical inference is defined in Section 8.

Log-transformed insulin lispro T_{max}, early 50% T_{max}, late 50% T_{max}, C_{max}, t_{1/2}, and AUC estimates will be evaluated to estimate geometric means, ratios of geometric means of insulin lispro within LY900014 to Humalog by day and bolus administration mode, and the corresponding 90% CIs of the ratios.

The statistical model for the Day 1 and Day 3 breakfast meal tests will include treatment (4 combinations of treatment and bolus administration mode: LY900014 dual-wave, Humalog dual-wave, LY900014 single-wave, or Humalog single-wave), period, day (Day 1 or Day 3), and treatment-by-day interaction as fixed effects and patient as a random effect.

Example SAS code:

```
proc mixed data=pk;
  class patient treatment period day ;
  model logpk = treatment period day treatment*day / ddfm=kr;
  lsmeans trt*day;
  random patient / grp= treatment;
  repeated / grp= treatment;
run;
```

A separate analysis model will be used for the Day 2 breakfast meal test, including treatment (4 combinations of treatment and bolus administration mode: LY900014 rapid, LY900014 standard, Humalog rapid, or Humalog standard, all given as a single-wave bolus) and period as fixed effects and patient as a random effect.

Example SAS code:

```
proc mixed data=pk;
  class patient treatment period;
  model logpk = treatment period / ddfm=kr;
  random patient / grp= treatment;
  repeated / grp= treatment;
run;
```

For the primary inference, insulin lispro administered from LY900014 will be concluded to have a significantly decreased early 50% T_{max} relative to Humalog if the upper confidence bound of the 2-sided 90% CI of the ratio of geometric means of the early 50% T_{max} is <1 .

If possible, the above models will also be used to calculate the intra-patient and inter-patient variability of LY900014, however if convergence issues occur, then the model will be appropriately updated to account for these issues.

As a sensitivity analysis, early 50% T_{max} will be analyzed by day using the Wilcoxon signed-rank test. The difference in median early 50% T_{max} between LY900014 and Humalog and the 90% CIs for the difference will be presented.

An exploratory analysis of Early 50% T_{max} , from breakfast on Days 1, 2 and 3 based on the standard single-wave data only will also be performed. The model will include sequence, treatment and day within period and treatment by day as fixed effects, and patient as a random effect.

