5.4. Scientific Rationale for Study Design

The study is a 4-period crossover design to reduce the variability of insulin PK and GD as each patient will act as his/her own control. On Days 1 and 3, each patient will undergo an insulin

administration using different bolus delivery modes (standard single-wave or standard dual-wave boluses) with LY900014 and Humalog before a solid, individually standardized breakfast test meal (MMTT) is administered; the standard dual-wave mode of administration will be compared to a standard single-wave (traditional) insulin administration via CSII. This design enables the optimization of a bolus delivery for both LY900014 and Humalog by monitoring the PK and GD properties (Luijf et al. 2013). To improve the comparability of the GD effects on Days 1 and 3, an overnight run-in period using a variable insulin and glucose IV infusion has been introduced. This run-in aims to achieve similar preprandial glucose levels for all patients before the start of the test meal and thereby reduces the variability of the postprandial glucose response. Insulin glulisine has been chosen for the IV optimization of plasma glucose during the run-in because insulin glulisine does not cross-react with the insulin lispro-specific assay used for the PK analysis. Because this run-in procedure requires a 7-hour fasting interval before the start of a test meal procedure, the run-in can only be implemented overnight and not for the planned lunch and dinner test meals. The run-in is also not implemented the night before the Day 2 test meal to better mimic the Phase 3 environment in which this meal will be used.

On Day 2, a high-glycemic index breakfast test meal will be administered, comparable to the one chosen for future Phase 3 studies, to test if a rapid or a standard single-wave bolus delivery will have an impact on the postprandial glucose excursions. Since LY900014 is a new formulation of the already marketed short-acting analog, Humalog, the latter is the best comparator to assess potential differences in clinical utility of this novel formulation.

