10.1. Sample Size Determination

An initial 24 patients may be randomized in order that approximately 20 patients complete the study. Twenty completing patients will provide approximately 80% power to demonstrate a 25% decrease in the time to early half-maximal concentration (early 50% T_{max}) between LY900014 and Humalog. Testing will be done at an α -level of 0.1 with a 2-sided confidence interval (CI). The variability was estimated by analyzing internal Lilly data (CCI [REDACTED]) for LY900014 and Humalog administered on CSII therapy, resulting in approximately 35.9% coefficient of variation of within-subject variability for early 50% T_{max} .

Patients who are randomized but drop out before completing assigned treatment may be replaced to ensure that approximately 20 patients complete the study (refer to Section 5.1).

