10.3.2.2. Pharmacokinetic Statistical Inference

Log-transformed insulin lispro T_{max} , early 50% T_{max} , late 50% T_{max} , C_{max} , and AUC estimates will be evaluated to estimate geometric means, ratios of geometric means of insulin lispro within LY900014 to Humalog, and the corresponding 90% CIs of the ratios.

The statistical model for the Day 1 and Day 3 breakfast meal tests will include treatment (4 combinations of treatment and bolus administration mode: LY900014 dual-wave, Humalog dual-wave, LY900014 single-wave, or Humalog single-wave), period, day-within-period, and treatment-by-day-within-period interaction as fixed effects and patient as a random effect. A separate analysis model will be used for the Day 2 breakfast meal test, including treatment (4 combinations of treatment and bolus administration mode: LY900014 rapid, LY900014 standard, Humalog rapid, or Humalog standard, all given as a single-wave bolus) and period as fixed effects and patient as a random effect. The variance-covariance structure considerations will be detailed in the statistical analysis plan. For the primary inference, insulin lispro administered from LY900014 will be concluded to have a significantly decreased early 50% T_{max} relative to Humalog if the upper confidence bound of the 2-sided 90% CI of the ratio of geometric means of the early 50% T_{max} is <1 .

As a sensitivity analysis, early 50% T_{max} will be analyzed using the Wilcoxon signed-rank test. The difference in median early 50% T_{max} between LY900014 and Humalog and the 90% CIs for the difference will be presented.

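### SAP 9.3.2: the text gives one random patient effect, but the example code gives each treatment its own; if followed, that covariance drops within-patient pairing and widens the primary 90% CIs

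*SAP*

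**What the plan says.** Protocol 10.3.2.2 gives patient as a random effect in both breakfast PK models and leaves the rest to the SAP: "The variance-covariance structure considerations will be detailed in the statistical analysis plan".

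SAP 9.3.2 repeats the single patient effect in words. For Days 1 and 3 the model has "treatment-by-day interaction as fixed effects and patient as a random effect"; for Day 2 it has "period as fixed effects and patient as a random effect". The example code beside each description says "random patient / grp= treatment", followed by a REPEATED statement grouped by treatment with no subject or type option. The Days 1/3 block also contains "lsmeans trt*day", although the variable is called `treatment` in its CLASS and MODEL statements.

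The same section asks these models, if possible, to yield intra- and inter-patient variability for LY900014, and adds that "if convergence issues occur, then the model will be appropriately updated to account for these issues". The primary rule is that the upper limit of the two-sided 90% CI for the early 50% Tmax ratio lies below 1.

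Two other places bear on the covariance. Protocol 5.4 justifies the crossover "to reduce the variability of insulin PK and GD as each patient will act as his/her own control". Protocol 10.1 (and SAP 7) bases power on "approximately 35.9% coefficient of variation of within-subject variability".

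**The concern.** In PROC MIXED, grouping the RANDOM statement by treatment gives each patient four independent effects, one per treatment-by-mode combination. The grouped residual is diagonal, so nothing restores a link between treatments. A patient's LY900014 and Humalog values then have modelled covariance zero, whereas the text's model gives them the between-patient variance as covariance.

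Text and code therefore give different confidence intervals for the primary decision, and the SAP does not say which governs. Under the code's structure the intervals would be those of four unrelated groups, and the precision for which the crossover was chosen would be missing from the reported limits. At stake are a real effect that is missed and ratios reported with needlessly wide intervals.

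**Working it through.** **Inputs.** Within-patient CV 35.9%, 20 completers, true ratio 0.75, two-sided α 0.1 (Protocol 10.1, SAP 7). The design is a four-period crossover in which each patient receives all four combinations. The between-patient CV is not in the documents, so a range of 10% to 50% is assumed.

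**1. The plan's own figure.** σW = √ln(1 + 0.359²) = 0.3482. Paired SE = σW·√(2/20) = 0.1101. Effect = −ln 0.75 = 0.2877. With 5% in the relevant tail and a noncentral t on 19 df, power = 0.809. This reproduces the stated 80%, and it does so with within-patient variance only, so it presumes that between-patient variance cancels.

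**2. The code's covariance, complete data.** The model-based SE becomes √[2(σW² + σB²)/20], with σW² = 0.1212 and σB² = ln(1 + CV²). The contrast weights are the same under either covariance, so the estimate is unchanged and its true SD stays 0.1101. Power is therefore Φ[(0.2877 − t·SE)/0.1101], with t = 1.686 on 38 df.

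| Assumed between-patient CV | σB² | Code SE | SE ÷ 0.1101 | Power |
|---|---|---|---|---|
| 10% | 0.0100 | 0.1145 | 1.04 | 0.805 |
| 20% | 0.0392 | 0.1267 | 1.15 | 0.750 |
| 30% | 0.0862 | 0.1440 | 1.31 | 0.658 |
| 40% | 0.1484 | 0.1642 | 1.49 | 0.539 |
| 50% | 0.2231 | 0.1856 | 1.69 | 0.410 |

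At CV 50%, an observed ratio of exactly 0.75 has upper limit exp(−0.2877 + 1.686 × 0.1856) = 1.03 and fails the rule. The paired limit is exp(−0.2877 + 1.729 × 0.1101) = 0.91.

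**3. Check by model fitting.** REML fits were run on simulated Days 1/3 data (20 patients, four treatments, two days, 1,000 runs per CV). SAS was not used, and fixed df stood in for Kenward-Roger. Over CV 10% to 50%:
- Code covariance: mean SE 0.115 to 0.187 against an actual SD of 0.108 to 0.111; 90% CI coverage 0.920 rising to 0.994; one-sided error 0.035 falling to 0.002.
- One shared patient effect with residual variances by treatment: power 0.81 to 0.83, coverage 0.90 to 0.91, one-sided error 0.044 to 0.057 (Monte Carlo SE about 0.007).

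**4. Missing meal tests.** Protocol 5.1.1.3 treats a Day 2 test as missing after glucose or insulin treatment in the six hours before the meal, so gaps can occur even in completers. With 10% of Day 2 tests missing at random (assumed), code power is 76%, 70%, 60%, 48% and 36% across the five CVs, against 77% to 78% with a shared effect. The estimate then also loses a little precision: at CV 50% its SD is 0.128 against 0.119.

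**5. Identifiability on Day 2.** Each patient has one value per treatment. The code has four patient and four residual variances, but only their four sums can be estimated. Heterogeneous compound symmetry (CSH) with a grouped residual has 4 + 1 + 4 = 9 parameters. The off-diagonals ρσiσj depend only on the four products √ρ·σi, so with the four diagonal terms only 8 quantities are identified. On Days 1/3 there are two values per patient per treatment, so the code's model can converge and the convergence sentence need never come into play.

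**The case against.** The blocks are labelled examples. They could not serve as printed, because the LSMEANS line names an undefined variable, and the prose in both documents consistently gives one patient effect. A reader might infer that the primary analysis will be run without pairing and that its intervals will be too wide. The documents do not establish that: it requires the example to be repaired and adopted, and the between-patient variance to be material. What remains is that the protocol hands the covariance structure to the SAP, and the SAP supplies it nowhere else.

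The grouping may be deliberate, since the SAP wants inter-patient variability for LY900014 and the exploratory objective compares it with Humalog. A plain shared effect gives one common variance and cannot deliver that. This is a fair objection to deleting the option and stopping there. It does not justify zero covariance, because treatment-specific variances can be estimated with the covariance kept.

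Days 1 and 3 of a period share treatment and catheter site. The code's patient-by-treatment effect absorbs that correlation, and a plain shared effect does not. A check with a shared effect and common residual, at assumed patient-by-period to residual variance ratios of 0.25 to 2, gave by-day coverage of 0.894 to 0.883 and one-sided error of 0.050 to 0.058. The harm to the planned by-day inference is small, but it supports offering a richer Days 1/3 model.

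Finally, the signed-rank sensitivity analysis is paired and could reveal a discrepancy. It would not change the primary interval.

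**Conclusion.** The contradiction between text and code is real and concerns the primary inference. If the code's covariance is used, any positive between-patient variance widens every LY900014/Humalog interval. The direction does not depend on assumptions; the size does. On the assumed range, power is between about 80% (CV 10%, where almost nothing is lost) and 41% (CV 50%), against 81% when paired.

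A reader might also infer that the trial is underpowered or that a positive finding would be unsafe. Neither follows. The stated power reproduces under the model in the text. The code's error is conservative, so a positive result obtained under it would stand, and complete-data point estimates are the same either way. This is an inconsistency that should be corrected before any PK model is run, not a threat to the validity of a positive claim.

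**What to change.** - **Primary inference, both blocks:** use `random patient;`. Keep the REPEATED statement grouped by treatment if treatment-specific residual variances are wanted. Change `trt*day` to `treatment*day`. The model text can then stay as it is.
- **Treatment-specific inter-patient variability:** use a separate or extended Days 1/3 model that keeps the cross-treatment covariance, for example `random treatment / subject=patient type=csh`, and align the text with it. This also allows for the correlation between Days 1 and 3 of a period. Do not combine CSH with a grouped residual on Day 2.
- **Convergence:** state that any fallback for the primary test must keep the shared patient effect.

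The cost is a few lines of code and text, and a second model if treatment-specific inter-patient variances are reported. No extra data are needed.

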To evaluate the difference in insulin lispro PK when LY900014 and Humalog are administered as different test bolus doses with an insulin pump to patients with T1DM during a breakfast meal test	AUC, C _{max} , T _{max} , early 50% T _{max} , and late 50% T _{max}
Secondary Objectives	Endpoints
To evaluate the sustainability of any difference in insulin lispro PK of LY900014 and Humalog over 3 days when administered as different test bolus doses with an insulin pump to patients with T1DM during a breakfast meal test	AUC, C _{max} , T _{max} , early 50% T _{max} , and late 50% T _{max}
To evaluate the difference in GD response when LY900014 and Humalog are administered as different test bolus doses with an insulin pump to patients with T1DM during a breakfast meal test	ΔAUC
To compare the durability of GD response over 3 days when LY900014 and Humalog are administered as different test bolus doses with an insulin pump to patients with T1DM during a breakfast meal test	ΔAUC
Exploratory Objectives	Endpoints
To evaluate the safety and tolerability of LY900014 administered with an insulin pump	Adverse events, anti-insulin lispro antibodies, infusion-site reactions/pain, and frequency and/or severity of hypoglycemia
To compare the GD response using CGM when LY900014 and Humalog are administered as different test bolus doses with an insulin pump to patients with T1DM during a standardized lunch meal	ΔAUC
To compare the GD response using CGM when LY900014 and Humalog are administered as different test bolus doses with an insulin pump to patients with T1DM during a standardized dinner meal	ΔAUC
To evaluate the intrasubject and intersubject insulin lispro PK variability of LY900014 compared with Humalog after 3 days of CSII	CV of AUC
To determine catheter occlusion rates with LY900014 and Humalog after 3 days of CSII	Microscopic assessment of infusion tubing after 3 days of use or in case of suspected catheter occlusion
To perform an exploratory comparison of glucose fluctuations with time in patients with euglycemia, hypoglycemia, and hyperglycemia receiving LY900014 and Humalog	CGM profiles during inpatient periods: time in euglycemia, hypoglycemia, and hyperglycemia

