4.3 Exploratory Objectives

- To evaluate the safety and tolerability of LY900014 administered with an insulin pump.
- To compare the GD response using continuous glucose monitoring (CGM) when LY900014 and Humalog are administered as different test bolus doses with an insulin pump to patients with T1DM during a standardized lunch meal.
- To compare the GD response using CGM when LY900014 and Humalog are administered as different test bolus doses with an insulin pump to patients with T1DM during a standardized dinner meal.
- To evaluate the inpatient and outpatient insulin lispro PK variability of LY900014 compared with Humalog after 3 days of continuous subcutaneous insulin infusion (CSII).
- To determine catheter occlusion rates with LY900014 and Humalog after 3 days of CSII.
- To perform an exploratory comparison of glucose fluctuations with time in patients with euglycemic, hypoglycemia, and hyperglycemia receiving LY900014 and Humalog.

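### The SAP's plan for intra- and inter-patient variability of AUC yields an arbitrary split on Day 2, pooled components under the model text, and a stated output for LY900014 only; the Days 1 and 3 code works, but in a narrow sense.

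*SAP*

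**What the plan says.** Protocol Section 4, Table ITSC.4.1, lists among the exploratory objectives: "To evaluate the intrasubject and intersubject insulin lispro PK variability of LY900014 compared with Humalog after 3 days of CSII". The endpoint is CV of AUC. Protocol 10.3.2.2 leaves the variance-covariance structure to the SAP.

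SAP 4.3 restates the objective as "To evaluate the inpatient and outpatient insulin lispro PK variability of LY900014 compared with Humalog". It keeps the comparison but changes the pair of terms. Protocol Section 2 schedules PK samples only on inpatient Days 1, 2 and 3.

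SAP 9.3.2 gives the only plan for splitting the variability: "If possible, the above models will also be used to calculate the intra-patient and inter-patient variability of LY900014", followed by "however if convergence issues occur, then the model will be appropriately updated to account for these issues". It does not mention Humalog, define either CV, name a day or give a method of comparison.

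For Days 1 and 3 the model text lists "period, day (Day 1 or Day 3), and treatment-by-day interaction as fixed effects", with patient as a random effect; the Day 2 text likewise has one patient effect. Neither mentions variances by treatment. The example code for both models contains "random patient / grp= treatment" and "repeated / grp= treatment", that is, a separate patient variance and a separate residual variance for each of the four product-by-mode combinations.

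**The concern.** Separating intra- from inter-patient variance needs replicate values from the same patient within whatever group has its own pair of variances. SAP Table 1 gives each patient each product-by-mode combination in one period only, so replication inside a group is absent on Day 2 and comes only from two days of the same period on Days 1 and 3. Text and code also describe different covariance structures, and the stated output covers one of the two insulins to be compared.

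At stake is the exploratory variability result. A Day 2 split could be reported as an estimate although the data do not determine it, and a Days 1 and 3 figure could be read as general within-patient reproducibility when it describes less than that.

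**Working it through.** **The plan's own figure.** The documents state no number for this objective. The nearest is the power for early 50% Tmax (SAP Section 7: 20 completers, within-patient CV 35.9%, ratio 0.75, two-sided alpha 0.1). Log-scale SD = √ln(1 + 0.359²) = 0.348; SE = 0.348 × √(2/20) = 0.110; |ln 0.75|/0.110 = 2.61. The noncentral t with 19 df gives 80.9%, so the stated 80% reproduces. It concerns another parameter and says nothing about AUC variability.

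**Design input.** SAP Table 1: four product-by-mode combinations over four periods, each once per patient. Values per patient per combination: 1 on Day 2, 2 on Days 1 and 3. Write τ²(g) for the patient variance and σ²(g) for the residual variance of combination g. Ranks below are of the REML information matrix for the variance parameters, with 20 patients over the four sequences.

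**Day 2 code.**
- Var(y) = τ²(g) + σ²(g). Covariance between a patient's values in different groups = 0, because the grouped RANDOM statement makes those effects independent.
- Eight parameters enter only through four sums: rank 4 of 8.
- One simulated data set (assumed true values: patient variance 0.16, residual 0.12), fitted from two starting points:

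| Start | Inter, 4 groups | Intra, 4 groups | Sums | Neg. log-likelihood |
|---|---|---|---|---|
| Low inter | 0.060, 0.058, 0.053, 0.057 | 0.354, 0.331, 0.256, 0.320 | 0.414, 0.390, 0.309, 0.377 | 10.04255 |
| High inter | 0.354, 0.331, 0.256, 0.320 | 0.060, 0.058, 0.053, 0.057 | 0.414, 0.390, 0.309, 0.377 | 10.04255 |

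With CV = √(exp(variance) − 1), the intra-patient CV of the first group is √(e^0.354 − 1) = 65.2% or √(e^0.060 − 1) = 24.9%, at the same likelihood.

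**Text models.** One patient variance and one residual variance: rank 2 of 2 for Day 2 and for Days 1 and 3. Both are estimable, but each is a single figure shared by LY900014 and Humalog.

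**Days 1 and 3 code.**
- Cov(Day 1, Day 3 | g) = τ²(g); Var(y) − Cov = σ²(g). Rank 8 of 8.
- Over 40 simulated trials (all variances assumed), each listed as two LY900014 groups then two Humalog groups: true inter 0.10, 0.10, 0.20, 0.20, mean estimates 0.101, 0.093, 0.207, 0.205; true intra 0.06, 0.06, 0.15, 0.15, mean estimates 0.058, 0.060, 0.167, 0.145. The text model gave one pair for the same data: 0.108 inter and 0.145 intra.
- Meaning: both values in a group come from one period on one catheter site (Protocol 5.1.1 and 7.1.3). So τ²(g) = patient + patient-by-treatment + patient-by-period variance, and σ²(g) is only Day 1-to-Day 3 variation within the period.

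**Precision.** With 20 patients, 20 Day 1-to-Day 3 differences per group leave 19 df. F(0.95; 19, 19) = 2.17, so the 90% CI of a variance ratio is the estimate divided or multiplied by 2.17, and of an SD ratio by √2.17 = 1.47, treating the two estimates as independent.

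**The case against.** A reader might infer that the comparison cannot be obtained at all, under text or code. The documents do not support that. The Days 1 and 3 code is full rank and prints components for Humalog as well as LY900014, because both statements are grouped by treatment. The omission of Humalog lies in one SAP sentence, not in that model's output.

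The protocol defers the covariance structure to the SAP, so the code can be read as that structure and the text as a generic description. That is a fair reading, but it still calls for the two to be aligned, and it makes the Day 2 problem the operative one.

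Neither document defines intra-patient as including period-to-period variation, and the objective refers to 3 days of CSII. Day 1-to-Day 3 variation on one catheter is therefore a possible meaning. This stands: the component is not shown to be biased, only narrow and unlabelled.

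It is also tempting to size the effect from the 35.9% planning CV. That CV is for early 50% Tmax, and no share of it is attributed to periods, so it does not measure the AUC endpoint.

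The plan is hedged, the code is labelled as an example, and the objective is exploratory. These lower the stakes. The hedge does not cure Day 2, however: its remedy depends on convergence problems, and in the simulation above the fit returned a different answer from each start at the same likelihood. The geometric CV% in SAP 9.1 covers both insulins but describes total spread only.

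**Conclusion.** The point holds in a limited form. Any intra/inter split from the Day 2 code is arbitrary; this follows from the design table and the code and needs no assumed variances. The text models give pooled components only and do not match the code. The SAP sentence names LY900014 although both documents set a comparison with Humalog. The Days 1 and 3 code does supply the comparison, by product and mode, provided its intra-patient part is read as within-period variation and its inter-patient part as including patient-by-period and patient-by-treatment variation.

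No AUC variance is given, so the size of any misstatement in the reported CVs is unknown; the simulated values show the mechanism only. The primary inference on early 50% Tmax is not affected by this route. The wording in SAP 4.3 is an editorial slip, since SAP 9.3.2 itself uses intra- and inter-patient.

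**What to change.** In SAP 9.3.2:

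1. Report intra- and inter-patient CV of AUC for both LY900014 and Humalog, with the ratio of intra-patient SDs and its 90% CI.
2. Take the within-period (Day 1-to-Day 3) components from the Days 1 and 3 code, and label them as such.
3. Do not report an intra/inter split from the current Day 2 code.
4. For Day 2 and for Day 3, add a model of log AUC with product-by-mode and period as fixed effects, correlated patient effects by product, and a residual variance by product (two levels). Each product then has two periods per patient, so both components are identified.
5. Align the model text with the code.

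In SAP 4.3, restore intrasubject and intersubject.

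The cost is one extra model and SAP wording, with no new data. The added model has downsides that the SAP should state. It assumes equal intra-patient variance across the two modes of a product. Those two periods use different modes (dual- versus single-wave on Day 3, rapid versus standard on Day 2), so its residual holds patient-by-mode as well as period-to-period variation, and intra-patient CV may be overstated. Precision is modest: about ×/÷ 1.47 on the SD ratio, slightly wider once period effects are estimated.
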